6.2.3. Study Medication Preparation

The study medications will arrive at the site prepared for instillation.

6.2.4. Study Medication Administration

During the Double-Masked Treatment Period, subjects will instill one drop of study medication in each eye at approximately 20:00 (± 60 min) and 08:00 (± 60 min) daily for 3 months.

6.2.5. Study Medication Accountability

The Principal Investigator is responsible for ensuring that an inventory is conducted upon receipt of the clinical supplies. The temperature chart recorder from the shipment will be deactivated, and the Investigator (or his/her designee) will verify that the temperature was maintained at 2° to 8°C (36° to 46°F) during transit. In the event of a temperature excursion or any study medications damaged during transit, the Investigator (or his/her designee) will notify Santen (or designee) and will not dispense the study medications until obtaining authorization from Santen (or designee). The receipt of clinical supplies form should be completed, signed, dated, and returned as directed. A copy must be maintained at the site for the Investigator's records.

The Investigator (or his/her designee) will keep a current record of the inventory, storage conditions and dispensing of all study medications. This record will be made available to Santen (or designee) for the purpose of accounting for all clinical supplies. Any significant discrepancy and/or deficiency must be recorded with an explanation.

All supplies sent to the investigational site must be accounted for and in no case will study medications be used in any unauthorized situation. It is the responsibility of the Investigator to ensure that any used and unused supplies are available to Santen (or designee) for accountability purposes throughout the study.

6.2.6. Study Medication Handling and Disposal

The used study medication kits will be stored at room temperature and the unused study medication kits will be refrigerated until final study medication accountability has been completed by Santen (or designee). Following final study medication accountability and

reconciliation by Santen (or designee), all used and unused study medication will be returned to the assigned central drug depot, or destroyed at the site at the direction of Santen.

6.2.7. Study Supplies

Customized blood sample collection kits for the PGx and urine pregnancy kit will be provided by Santen (or designee).

6.3. Concomitant Medications or Therapies

Medication or therapy considered necessary for the subject's welfare may be given at the discretion of the Investigator. Subjects may continue participation in the study if the instituted medication or therapy will not interfere with the evaluation of the study medication. Whenever possible, medications should be administered in dosages that remain constant throughout the study. Any treatment other than the study medication during the study duration will be considered as a concomitant treatment. The information of concomitant treatment must be recorded in the subject's source documents and on the eCRF.

- Concomitant medication: name of medication, route of administration, treated eye(s) (if applicable), dose, frequency, indication, start date, and stop date.
- Concomitant therapy: name of therapy, treated eye(s) (if applicable), indication, start date, and stop date.

6.3.1. Prohibited Medications or Therapies

- All ocular medications other than sodium chloride/potassium chloride ophthalmic solution, cataract treatment agents (e.g., glutathione, pirenoxine), Vitamin B₁₂ formulation (e.g., cyanocobalamin), over-the-counter dry eye artificial tears/drops, and study medications during the study duration.
 - If artificial sodium chloride/potassium chloride ophthalmic solution, cataract treatment agents, Vitamin B₁₂ formulation, over-the-counter dry eye artificial tears/drops are concomitantly used, there must be an interval of **at least 10 minutes** between use of the study medication and these ocular medications (the study medication to be given first).
- All systemic medications for ocular hypotensive (e.g., oral or intravenous CAI, oral glycerol) during the study duration.
- Any ocular, periocular, inhaled, nasal, or systemic corticosteroids (excluding joint injection), etc. during the study duration.
- Lacrimal/punctual occlusion via plug (s) or cautery during the study duration.
- Initiate or modify any systemic or topical medication known to affect IOP (e.g., β -adrenergic antagonists, α -adrenergic agonists, calcium channel blockers, ACE inhibitors, and ARB) within the first 28 days prior to Visit 2 (Baseline, Day 1) and during the study duration.

- Contact lenses within 1-2 weeks prior to Visit 2 (Baseline, Day 1) until end of treatment in either eye (1 week for soft contact lens wearers, and/or 2 weeks for rigid contact lens wearers).
- Any ocular surgery or ocular laser treatment within 180 days prior to Visit 2 (Baseline, Day 1) and throughout the study in either eye.
- Participation in other investigational drugs (oral or topical therapy) or device clinical trials within 28 days prior to Visit 2 (Baseline, Day 1) and/or participation in other investigational drugs (intravitreal injection therapy) within 3 months or 5 half-lives (whichever is longer) prior to Day 1 or planning to participate in other investigational drug or device clinical trials during a time which would overlap with the duration of the study. This includes both ocular and no-ocular clinical trials. Exposure to investigational biologics should be discussed with the medical monitor.

The decision to administer a prohibited medication or therapy should be made with the safety of the subject as the primary consideration. Whenever possible, Medical Monitor or designee should be notified before any prohibited medication or therapy is administered. There may be additional prohibited therapies not mentioned above. Medical Monitor or designee should be contacted if the permissibility of a specific medication or therapy is in question.

6.4. Treatment Compliance

To obtain reliable efficacy and safety data, the following precautions will be taken to ensure compliance with the treatment regimen during the study:

- Subjects will receive verbal and written instructions for proper instillation of the study medication, the dosing regimen, and the conditions of the study medication storage.
- Subject will record daily medication instillation into paper subject diary.
- Subjects will be reminded at study visits to consistently dose at the same time of the day
 - Twice daily at 08:00 and 20:00 [$\pm 60\text{min}$] through Visit 2 (Baseline, Day 1) to Visit 5 (Month 3).
- Subjects will be reminded of the evening instillation of the study drug on the day before Visit 3 (Week 2) through Visit 5 (Month 3)/Early Termination respectively.
- Subjects will be reminded that the morning instillation of the study drug at each visit through Visit 3 (Week 2) to 5 (Month 3) will be done at the site.
- Subjects will be queried regarding compliance with the protocol's dosing regimen at Visit 3 (Week 2) through Visit 5 (Month 3)/Early Termination.
- Subjects will be counseled on proper dosing procedures and dosing schedule if the subject's compliance is not 100%.
- A subject's dosing compliance for a specific period is determined by the total number of days that subject followed the proper dosing procedures and dosing schedule. Stoppage of study medication use, overdosing of study medication, incorrect time of

study medication administration, will be noted as non-compliance. The subject's dosing compliance will be recorded in the subject's source documents at Visit 3 (Week 2) through Visit 5 (Month 3)/Early Termination.

- Subjects may be discontinued from the study at the discretion of the Investigator if the subject cannot be brought into compliance.

6.5. Randomization and Masking

A stratified permuted-block randomization will be employed to randomize eligible subjects in a 1:1 ratio to either DE-126/Vehicle arm or Timolol Maleate arm. The randomization will be stratified by mean diurnal IOP in the study eye at baseline visit (Visit 2): <25 mmHg vs. \geq 25 mmHg.

The randomization schedule will be generated and implemented using central randomization via Interactive Response Technology (Medidata Rave RTSM). Each randomized subject will receive numbered study medication kits as assigned by Medidata Rave RTSM.

This is a double-masked study. The subjects, Investigators, Examiners, and Santen personnel involved in the conduct of the study will be masked to the study treatment. An authorized unmasked study staff member at the investigative site who is not the Investigator or Examiner will dispense and collect study medication(s) and will query about dosing compliance.

Subjects will be instructed not to show the eye drop bottles or discuss the eye drop to either the Investigator or the Examiner or other study subjects. The active control treatment (Timolol Maleate) containers will be over-labeled and packaged in the same secondary package (e.g., cardboard kit carton) as the investigational treatment (DE-126). Subjects on DE-126/Vehicle arm will receive a kit containing 2 bottles labeled "morning" for the morning dose and 2 bottles labeled "evening" for the evening dose. Subjects on Timolol arm will receive a kit containing 2 bottles labeled morning/evening for the BID dosing.

Each eligible subject will receive a numbered study medication kit assigned by Central randomization via Interactive Response Technology (Medidata Rave RTSM) at Visit 2 (Baseline, Day 1) and at Visit 4 (Week 6).

In case of a medical emergency, the Principal Investigator may reveal the treatment information by unmasking through Medidata Rave RTSM to know which treatment the subject has received. The Principal Investigator (or his/her designee) should contact Santen, or Santen's designee, before taking this measure, if there is sufficient time. Santen, or Santen's designee, must be informed of all instances where the code is broken and of the reasons for such instances.

Additionally, the AE or SAE for which study treatment was unmasked should be reported to Santen Pharmacovigilance.

7. DISCONTINUATION OF INVESTIGATIONAL PRODUCT AND SUBJECT DISCONTINUATION/WITHDRAWAL FROM STUDY

7.1. Subject Early Discontinuation/Withdrawal from the Study

An early termination occurs when a subject who provides written informed consent ceases participation in the study, regardless of circumstances, before the completion of the study. Subjects may be voluntarily discontinued from study medication or withdrawn from the study at any time for any reason. In addition, the Principal Investigator or Medical Monitor or designee may discontinue the study drug administration or terminate a subject's study participation due to any of the following reasons:

- AE (e.g., not compatible with study continuation)
- Non-compliance with study drug
- Lack of efficacy (e.g., IOP exceeds 34 mmHg in either eye after randomization)
- Progressive disease
- Protocol deviation (e.g., not fulfilling eligibility criteria)
- Pregnancy
- Voluntary withdrawal by subject at any time for any reason
- Lost to follow-up (e.g., no contact is possible)
- Death
- Other

If the study drug administration is discontinued prior to Visit 5, they should be encouraged to still participate in all follow-up study visits until Visit 5 on an observational basis.

If the study drug administration is discontinued prior to Visit 5, then to the extent possible, all procedures for Early Termination will be performed on the day of early drug discontinuation as per [Table 3](#). Subjects who are discontinued from the study early will not be replaced.

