4.4. Schedule of Events and Procedures

The schedule of events and procedures is provided in [Table 3](#).

Table 3: Schedule of Events and Procedures

	Washout Period		Double-Masked Treatment Period				Follow-up Period
	Visit 1 Screening *	Optional Visit 1a	Visit 2 Eligibility/Baseline *	Visit 3 Week 2	Visit 4 Week 6	Visit 5 Month 3 Exit or Early Termination ^a	2 weeks of post-Last Study Drug Administration
Study day	D-28		D1	D14	D42	D90	Study Exit + D14
Visit window in days	+7		NA	±3	±3	±7	+7
Signed and dated informed consent ^b	X						
Inclusion/Exclusion Criteria ^b	X		X				
Demographics and Medical History, including prior PGA ^c	X						
Other prior or Concomitant Medications/ and Therapies/Procedures	X	X	X	X	X	X	
Dosing Compliance Check				X	X	X	
AEs ^d	X	X	X	X	X	X	X
Pregnancy Test ^e	X		X		X	X	
Vital Signs (blood pressure/pulse rate) ^f	X		X (08:00)			X (08:00)	
Refraction ^g	X						
BCVA ^g	X	X	X (08:00)	X (08:00)	X (08:00)	X (08:00)	
Slit-lamp Biomicroscopy ^h	X	X	X (08:00)	X (08:00)	X (08:00)	X (08:00)	
IOP ⁱ	X	X	08:00	08:00	08:00	08:00	
			10:00	10:00	10:00	10:00	
			16:00	16:00	16:00	16:00	
Pachymetry ^j	X						
Instill study medication after IOP measurement at site by unmasked site staff and record dosing				X (08:00)	X (08:00)	X (08:00)	
Gonioscopy ^k	X						
Visual Field ^l	X						

Table 3: Schedule of Events and Procedures (Continued)

	Washout Period		Double-Masked Treatment Period				Follow-up Period 2 weeks of post-Last Study Drug Administration
	Visit 1 Screening	Optional Visit 1a	Visit 2 Eligibility/Baseline	Visit 3 Week 2	Visit 4 Week 6	Visit 5 Month 3 Exit or Early Termination ^a	
Study day	D-28		D1	D14	D42	D90	Study Exit + D14
Visit window in days	+7		NA	±3	±3	±7	+7
Ophthalmoscopy ^m	X		X (16:00)			X (16:00)	
Blood Sampling for PGx ⁿ						X	
Dispense Study Medication & Diary			X		X		
Collect Study Medication & Diary					X	X	
Phone call ^o				X	X	X	X
GQL-15 questionnaire ^p			X			X	

* Visit 1 (Screening) and Visit 2 (Eligibility/Baseline, Day 1) may be combined into one visit for treatment-naïve subjects as long as the additional requirements of Visit 2 (Eligibility/Baseline, Day 1) are fulfilled on the day of this combined visit; in particular, full diurnal IOP measurements (at 08:00, 10:00, 16:00) must be taken.

^a Optional at unscheduled visit, required for early terminated subjects.

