8. STUDY ASSESSMENTS AND PROCEDURES

8.1. Visit Details

The Schedule of Events and Procedures [Table 3](#) provides a high-level overview of the visits. The sections below provide visit guidance/details by visit.

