8.1.6. Visit 5 (Month 3, Day 90 ±7) / Study Exit/ Early Termination

- Update concomitant medications and procedures/therapies.
- An authorized unmasked study staff member, other than the Investigator or Examiner should query the subject regarding dosing compliance and check the subject paper diary of daily medication recording.
- Query the subject regarding AEs.
- As per Schedule of Events and Procedures ([Table 3](#)), perform the following procedures or assessments immediately before the 08:00 (±60 min) IOP measurement (all ophthalmic procedures to be performed in both eyes):
 - BCVA (before the 08:00 (±60 min) IOP measurement)
 - If more than 10 letters in BCVA were lost compared to the screening visit, then refraction should be performed again.
 - Slit-lamp biomicroscopy (before the 08:00 (±60 min) IOP measurement)
 - Perform vital signs (blood pressure/pulse rate) measurements (before the 08:00 (±60 min) IOP measurement).
 - Obtain urine and perform a urine pregnancy test, if the subject is a female of childbearing potential (before the 08:00 (±60 min) IOP measurement).
- Perform IOP measurement at 08:00 (±60 min).
- Instill study medication/eye drop after the 08:00 IOP measurement in both eyes. Authorized unmasked study staff should make sure the instillation is performed. Record the morning medication in subject diary.
- Perform IOP measurement at 10:00 (±60 min), and 16:00 (±60 min).
- Perform pupil dilation in both eyes after the 16:00 (±60 min) IOP measurement.
- Perform ophthalmoscopy with pupil dilation in both eyes immediately after the 16:00 IOP measurement.
- Perform GQL-15 questionnaire at any time during this visit.
- An authorized unmasked study staff member, other than the Investigator or Examiner, must:
 - Collect all used and unused bottles of study medication.
 - Collect the paper subject diary.

- If the subject provided written consent to provide a blood sample for a future PGx laboratory research study, the sample must be collected at this visit, if not collected at the previous visits.
- Exit the subject from the study.
- Inform the subjects they will be contacted to confirm AEs by phone call approximately 2 weeks post last study drug administration.

Note:

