- **If the study drug administration is discontinued prior to Visit 5, then to the extent possible, all procedures for Study Exit/Early Termination as per Table 3 will be performed on the day of early termination. Subjects who are discontinued from the study early will not be replaced.**
- **If subject requires an unscheduled visit, procedures and assessments will be performed as needed.**

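### Protocol 8.1.6, followed literally, exits subjects who stop study drug early, although Protocol 7.1 wants them followed to Visit 5

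*Protocol*

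**What the plan says.** **Protocol 7.1** treats stopping study drug and leaving the study as different events. It defines the second: "An early termination occurs when a subject who provides written informed consent ceases participation in the study". For subjects whose drug is stopped before Visit 5, it says "they should be encouraged to still participate in all follow-up study visits until Visit 5 on an observational basis". The next paragraph has the same trigger and says that, as far as possible, "all procedures for Early Termination will be performed on the day of early drug discontinuation as per" Table 3.

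**Protocol 4.4, Table 3** has one final column for Visit 5, exit and early termination. Footnote a to that column reads "Optional at unscheduled visit, required for early terminated subjects". The column includes the row "Instill study medication after IOP measurement at site by unmasked site staff and record dosing" at 08:00. No row says that the subject is exited.

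**Protocol 8.1** calls Table 3 a high-level overview and adds: "The sections below provide visit guidance/details by visit".

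**Protocol 8.1.6** is one list for Visit 5, Study Exit and Early Termination. One bullet, with no condition, is "Exit the subject from the study". The closing Note is triggered by drug being stopped before Visit 5 and says that, as far as possible, "all procedures for Study Exit/Early Termination as per Table 3 will be performed on the day of early termination". The Note does not repeat the request to keep the subject in follow-up.

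**Analysis.** Protocol 9.7 censors IOP after a drug stop only where other IOP-lowering medication or surgery is used. SAP 8.1.1.1 censors only after rescue therapy. SAP 3.4 links the early termination visit to the end of study participation.

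**The concern.** A coordinator whose subject has just stopped drug is sent by 8.1 to the visit sections. The only detailed early termination list is in 8.1.6. Its Note says the stop day is the day of early termination, which in 7.1 means that participation has ended, and its list says to exit the subject. Nothing there says that the exit step does not apply to a subject who will keep attending. Followed step by step, 8.1.6 undoes the retention request in 7.1.

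The data at stake belong to the primary endpoint. An off-drug IOP without rescue enters the primary MMRM if it is collected, and an exit turns it into a missing value. When the stop-day visit falls in the same analysis window as a scheduled visit still to come, exit also decides which of the two is analysed.

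**Working it through.** **Step 1: the texts for one trigger, drug stopped before Visit 5.**
- 7.1, first sentence: keep attending to Visit 5.
- 7.1, second sentence: do the early termination assessments in Table 3 on the day of drug stop. This is compatible with the first sentence, because Table 3 has no exit row.
- 8.1.6 Note: do the Table 3 assessments, on a day labelled as early termination.
- 8.1.6 list: exit the subject, without exception.

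The two sentences of 7.1 fit together. The exit bullet and the Note's label do not fit with 7.1.

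**Step 2: are the data used?** Without rescue, yes (Protocol 9.7, SAP 8.1.1.1). After rescue, values are censored whether the subject stays or leaves, so exit costs no usable post-rescue primary value.

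**Step 3: values affected per subject.** Inputs:
- SAP Table 2 windows: Week 2 = Days 2–25, Week 6 = Days 26–61, Month 3 = Day 62 onward; targets are Days 14, 42 and 90.
- SAP 4.1.6: a visit with all three IOPs is preferred; among complete visits in one window, the one closest to target is used.
- Three IOPs per visit and three visits give 3 × 3 = 9 primary values.

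Assumptions: no rescue, a subject willing to stay, scheduled visits on their target days, and scheduled visits up to the stop completed. The table compares a subject exited at drug stop with the same subject retained. Columns 2 and 3 assume a complete stop-day visit; column 4 assumes no stop-day IOPs beyond any scheduled visit already done.

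| Stop day | Values lost by exit | Values from the stop day instead of the scheduled visit | Values lost if stop-day IOPs are missing |
|---|---|---|---|
| 2–13 | 6 | 3 (Week 2) | 9 |
| 14–25 | 6 | 0 | 6 |
| 26–41 | 3 | 3 (Week 6) | 6 |
| 42–61 | 3 | 0 | 3 |
| 62–89 | 0 | 3 (Month 3) | 3 |

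Example, stop on Day 30. If exited, the stop-day visit supplies Week 6 and Month 3 is missing: 3 lost. If retained, the Day 42 visit is closer to target, so it supplies Week 6, and Day 90 supplies Month 3.

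**Step 4: scale, for illustration only.** The documents give no rate of unrescued subjects who stop drug and would stay. Assume that 1% to 5% of 294 (0.01 × 294 ≈ 3; 0.05 × 294 ≈ 15) were exited this way. Planned values: 294 × 9 = 2,646.
- All stops by Day 25, complete stop-day visits: 3 × 6 = 18 (0.7%) to 15 × 6 = 90 (3.4%).
- All stops before the Week 2 visit, no stop-day IOPs: 3 × 9 = 27 (1.0%) to 15 × 9 = 135 (5.1%).

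Stops spread over the three months would lose fewer.

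**The case against.** The best answer is that the protocol can be read without conflict. 7.1 addresses this exact case and puts retention first. Both 7.1 and the Note point to Table 3, which has no exit row, so the sensible reading is to assess on the stop day and then continue. The analysis text expects this: Protocol 9.7 speaks of IOP collected after drug discontinuation, and SAP 7.6 has a compliance formula for visits after drug withdrawal. Sites are also trained and monitored. All of this stands, and it shows what the sponsor intends. It does not remove the unconditional exit step from the list that 8.1 sends sites to, and no text tells them to skip it.

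Three stronger readings may tempt a reader, and the documents do not support them:
- *The early termination column is only for subjects who leave.* Footnote a also allows it at unscheduled visits, and 7.1 and the Note both apply it at drug stop. SAP 3.4 ties the visit to the end of participation but is silent on subjects who stop only the drug.
- *Sites are told to dose a subject who has just stopped.* The instillation row is in the column with no stated exception, but both 7.1 and the Note limit the procedures to what is possible. This is untidy wording, not an instruction to dose.
- *A late stop costs nothing.* The zero loss from Day 62 holds only if the stop-day IOPs are complete. Otherwise the three Month 3 values are missing.

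**Conclusion.** The point holds as a minor contradiction between two operative sections. The protocol does not prescribe early exit, but 8.1.6 taken literally produces it, and the wording leaves about 45 sites to work out that one bullet does not apply.

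For an unrescued subject who would have stayed, with a complete stop-day visit and visits on target days, exit costs 6 of 9 primary values for a stop by Day 25, 3 of 9 for Days 26–61, and none from Day 62. It costs more if stop-day IOPs are missing. That some sites would act this way is inference. The number of subjects is unknown, and the overall effect is probably small.

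A reader might infer that the non-inferiority conclusion is at risk. The documents do not show this: they give no rate of such stops, and the IOP values that would be lost are unknown.

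**What to change.** In Protocol 8.1.6:
1. Limit the exit step to subjects who complete Visit 5 or whose study participation ends. The second group covers withdrawal by the subject, loss to follow-up, death, a decision by the investigator or Medical Monitor to end participation, study or site closure, and pregnancy. On pregnancy, one bullet of 8.6.4.2 offers drug stop and/or withdrawal, but its fuller paragraph on female subjects requires both.
2. In the Note, replace the day of early termination with the day of early drug discontinuation, to match 7.1.
3. Add to the Note that subjects who stop only study drug then continue the remaining scheduled visits to Visit 5, with no study-drug instillation or dispensing.

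This takes a few lines and needs no new visit type and no change to the analysis. The cost is a few more off-drug visits, which 7.1 already requests.
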